9.3 Definition of Baseline

Baseline measure for the primary efficacy endpoint is defined as pre-randomization measurement taken at Visit 2 (Day 1, [REDACTED]). If a measure is taken both [REDACTED] and [REDACTED] the baseline will be the time-point-matched measure at Visit 2 (Day 1). For changes from [REDACTED] to [REDACTED] after the first treatment, the change from [REDACTED] to [REDACTED] at Visit 2 (Day 1) will be considered the baseline value.

For measures from patient daily diaries in the secondary and exploratory endpoints, baseline is defined as the average of all days during Day -7 to Day -1, calculated separately for the morning, bedtime, and daily averages. Daily scores are first obtained by averaging the AM and PM scores for that day, as applicable.

9.4 Data Analysis Conventions

All data analysis will be performed by [REDACTED] after the study is completed and the database has been locked and released for unmasking. Statistical programming and analyses will be performed using SAS Version

9.4 or higher. Output will be provided in rich text format (RTF) for tables and portable document format (PDF) for tables, listings, and figures using landscape orientation.

Summaries for continuous and ordinal variables will include the number of observations (n), mean, SD, median, minimum, and maximum. Minima and maxima will be reported with the same precision as the raw values; means, confidence intervals (CI), and medians will be presented to one additional decimal place than reported in the raw values. SDs will be presented to two additional decimal places than reported in the raw values. Summaries for discrete variables will include counts and percentages. CFB will be calculated as follow-up visit value minus baseline value. Differences between active treatment and placebo groups will be calculated as active minus placebo.

All statistical tests will be two-sided at a significance level of 0.05 unless otherwise specified. CIs for differences between treatment groups will be two-sided at 95% confidence. All p-values will be rounded to 3 decimal places; p-values less than 0.001 will be presented as “<0.001”; p-values greater than 0.999 will be presented as “>0.999.”

Unless otherwise specified, summaries will be presented by treatment group and, where appropriate, visit. All study data will be listed by subject, treatment, and visit (as applicable) based on all randomized patients unless otherwise specified.

9.5 Adjustments for Multiplicity

Hierarchical fixed sequence testing strategy will be used in the analysis of the primary dry eye sign endpoint and the secondary dry eye symptom endpoint to maintain study-wide Type I error at one-sided 0.025. If the primary endpoint is statistically significant, then the study will be declared a success for the primary endpoint, and the secondary endpoint will be evaluated. If the primary endpoint analysis is not statistically significant, no claim will be made for the secondary endpoint.

10 Disposition of Patients

Patient disposition will be presented in terms of the numbers and percentages of patients who were screened and who screen failed; who were randomized; who were included in each analysis population (ITT, PP, and Safety); and who completed the study, discontinued from the study, and discontinued from the study due to COVID-19. Disposition will be summarized by treatment group and the overall total for all screened patients. Percentages will be calculated using all randomized patients as the denominator unless otherwise specified.

The reasons for premature study discontinuation, both general and COVID-19 related, will be summarized by treatment group and the overall total for all randomized patients and include: AEs, protocol violation, administrative reasons, lack of efficacy, lost to follow-up, pregnancy, sponsor termination of study, withdrawal by subject, and other. Percentages will be calculated using randomized patients as the denominator. A patient listing will be provided that includes the date of and reason for premature study discontinuations.

The number and percentage of patients with any deviation, major deviation, and minor deviation will be summarized by treatment group as well as overall total for all randomized patients. The protocol deviations that will be summarized include the following categories: Informed Consent, Inclusion/Exclusion and Randomization, Test Article / Study Drug Instillation and Assignment at Site, Improper Protocol Procedures at Site (Missed, Repeated, Not Per Protocol), Site's Failure to Report SAE (Serious AE) / AE, Visit out of Window (Missed, Early, Late), Subject's Non-compliance with Test Article / Study Drug, Subject's use of Prohibited Concomitant Medication, Subject's Failure to Follow Instructions, and Other. A subject listing will be provided that includes the date of the deviation, visit at which the deviation occurred, the deviation code, the deviation description, the action taken, if the deviation was COVID-19 related, and the classification of whether the deviation was judged to be major or minor in a masked review.

In addition, subject listings will be provided that include randomization schedule details, informed consent date, inclusion and exclusion criteria violations, and exclusions from the analysis populations.

11 Demographic and Pretreatment Variables

11.1 Demographic Variables

The demographic variables collected in this study include age, sex (childbearing potential), race, ethnicity, and iris color. Patients who record more than one race will select Other and specify their racial identities.

Iris color will be summarized by OD and OS. Demographic variables will be summarized separately for the ITT, PP, and Safety populations.

Age (years) will be summarized, by treatment group and the overall total among all patients in the respective summary population, using continuous descriptive statistics (number of patients [n], mean, SD, median, minimum, and maximum). Age will also be categorized as follows: < 65 years and \geq 65 years. Age will be reported in years and calculated using the following formula:

$$\text{Age} = (\text{Informed Consent Date} - \text{Date of Birth}) / 365.25$$

The number and percentage of patients will be presented, overall and by treatment, for age category, sex, race, ethnicity, iris color, and childbearing potential (among female patients).

A subject listing that includes all demographic variables will be provided.

11.2 Baseline Disease Characteristics

Baseline disease characteristics will be summarized for all assessments including tCFS and fluorescein staining, ocular discomfort and dryness bedtime average, [REDACTED] Ocular Discomfort & 4-Symptom Questionnaire, lissamine green staining, TFBUT, conjunctival redness, total and subtotal OSDI score, and [REDACTED] Ocular Discomfort Scale by region, symptom, or question where relevant. Summaries will be presented for the study eye only for assessments used in efficacy endpoints except ocular discomfort & 4-symptom questionnaire and OSDI efficacy endpoints for subject-level. Continuous endpoints will be

summarized using continuous descriptive statistics (number of patients (n), mean, SD, median, minimum, and maximum). Baseline disease characteristics will be summarized separately for the ITT, PP, and Safety populations.

12 Medical History and Concomitant Medications

12.1 Medical History

Medical history will be coded using Medical Dictionary for Regulatory Activities (MedDRA) Version 25.0.

The number and percentage of patients with ocular and non-ocular medical history will be summarized separately and presented by treatment group and overall total at the subject level by System Organ Class (SOC) and Preferred Term (PT) using the ITT population. If a subject reports the same PT multiple times within the same SOC, that PT will only be counted once within that SOC. As with the PT, if a subject reports multiple conditions within the same SOC, that SOC will only be reported once. SOCs will be displayed in internationally agreed order and PTs within a SOC will be listed in order of descending frequency across all patients.

Listings of medical history will be generated separately for ocular and non-ocular data for all randomized patients.

12.2 Concomitant Medications

Concomitant medications will be coded using World Health Organization Drug Dictionary (WHODrug) Global (B3, March 2022) and summarized to the therapeutic drug class (Anatomical Therapeutic Chemical [ATC] 4 classification) and preferred name. If the ATC 4 classification is not provided, then the next lowest classification that is provided in the coding dictionary will be used.

Concomitant medications are defined as those having been taken (1) prior to initiation of randomized study drug administration and continuing for any period of time following the first administration of randomized study drug or (2) at any time following the first administration of randomized study drug.

Ocular and non-ocular concomitant medications will be summarized using the ITT population. Medications will be tabulated for each treatment group and overall total using frequencies and percentages. Patients may have more than one medication per ATC text. At each level of subject summarization, a subject will be counted once if they report one or more medications. Percentages will be based on the number of patients in each treatment group. ATC classes will be listed in order of alphabetically and will be displayed with ATC text. Preferred names within an ATC class will be listed in descending frequency across all patients.

Listings of concomitant medications will be generated separately for ocular and non-ocular concomitant medications for all randomized patients.

12.3 Concomitant Procedures

Concomitant procedures/surgeries data will be coded using MedDRA v25.0. A listing of concomitant procedures/surgeries will be provided separately for ocular and non-ocular data for all randomized patients.

13 Dosing Compliance and Treatment Exposure

Subject listings will be produced for run-in and study drug assignment, instillation, and accountability.

13.1 Dosing Compliance

Patients will be instructed on proper use of the patient daily diary and proper instillation and storage of study drug at the end of Visit 1 (Day -14) through Visit 6 (Day 57) and given written instructions.

To account for diary entries that may be made after midnight nominally for the preceding evening, an evening diary entry with a dosing time on or after midnight but before 3 AM will be summarized as an entry for the preceding evening.

In the patient symptom daily diary, if more than 25% of applicable Dose Taken boxes are checked "No", left blank, or missing for a diary period, that patient will be deemed non-compliant and a dosing deviation will be recorded. These guidelines will be used by the Investigator for determining the patient's necessary compliance for the study and for recording deviations from this compliance.

Dosing compliance (% compliance) will be assessed by calculating the number of actual doses received and comparing that to the number of expected doses as follows:

$$\text{Compliance (\%)} = \frac{\text{Number of Actual Doses Received}}{\text{Number of Expected Doses}} \times 100\%$$

The number of actual doses received will be calculated as the sum of the number of doses reported in the diary, plus the dose reported in the Study Drug Assign/Instill eCRF. If a subject received study drug in one eye but not the other, the subject will be counted as having dosed at that visit.

The number of expected doses that will be used for calculating compliance will be calculated as:

$$\text{Number of Expected Doses} = 4 \times [\text{Date of Last Dose} - \text{Date of Visit 2 (Day 1)} + 1]$$

for all patients.

A categorical dosing compliance variable will also be derived for <75%, 75% to 125%, >125%, where the category, 75% to 125%, is considered compliant.

Dosing compliance (%) will be summarized with continuous descriptive statistics (number of patients [n], mean, SD, median, minimum, and maximum) for each treatment group and for all patients using the Safety population. The compliance categories defined above will be summarized categorically with counts and percentages of those who were non-compliant, compliant, and over-compliant.

A subject listing of dosing compliance as well as treatment exposure (described below) will also be produced for all randomized patients.

13.2 Treatment Exposure

Extent of treatment exposure for completed or discontinued patients will be calculated in days using the following:

$$\text{Extent of Exposure (days)} = [\text{Date of Last Dose} - \text{Date of Visit 2 (Day 1)}] + 1$$

Extent of treatment exposure for patients who were lost to follow-up will be calculated in days using the following:

$$\text{Extent of Exposure (days)} = [\text{Date of Last Recorded Visit} - \text{Date of Visit 2 (Day 1)}] + 1$$

Extent of treatment exposure for each subject exposed to study drug will be summarized with continuous descriptive statistics (number of patients (n), mean, SD, median, minimum, and maximum) for each treatment group and overall total for all patients using the Safety population. Additionally, total exposure in days will be summarized for each treatment group and overall total for all patients.

14 Efficacy Analyses

14.1 Primary Efficacy Endpoint

14.1.1 PRIMARY ANALYSIS METHODS

Primary analysis of the CFB [REDACTED] to Day 29 [REDACTED] in tCFS will be performed using an Analysis of Covariance(ANCOVA) model adjusted for baseline value with treatment group as the explanatory variable on ITT population with Estimand 1 or ITT population with Estimand 2 depending on the rate of intercurrent events. Least squares (LS) means for each treatment group and the LS mean difference comparing 0.3% SI-614 with placebo will be presented from the model together with SEs, two-sided 95% CIs, and one-sided p-values.

Subject listings will be provided for the primary efficacy endpoint for all randomized patients.

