8.1.4 Procedures for Final Study Entry

Patients must meet all inclusion and none of the exclusion criteria.

8.1.5 Methods for Assignment to Treatment Groups:

At Visit 1, patients who provide written informed consent will be assigned a unique 5-digit screening number, which includes the 2-digit site number plus a unique 3-digit screening number beginning with 001 (eg, 11-001, 11-002, 11-003, etc.). Screening numbers must be assigned in ascending consecutive order.

Prior to Visit 2, the Medical Monitor will review the medical and medication history, screening results and screening eligibility criteria for each patient who enters the run-in period, and confirm the patient's eligibility for the study. If there is a change in medical or medication status between Visits 1 and 2, the Medical Monitor will review and confirm the patient's eligibility for the study prior to randomization at Visit 2 (if possible) or as soon as possible after Visit 2.

At Visit 2, a patient who meets all the eligibility criteria will be randomized to receive treatment with 0.3% SI-614 or placebo in a 1:1 ratio. The Interactive Voice/Web Response System (IVRS/IWRS) will be used to account for the stratification factors.

Patient's will be stratified by the following factors and cut-offs:

1. Average of dryness and ocular discomfort at bedtime assessment for Run-in patient daily diary mean (Day -7 through Day -1).
 - a. ≤ 2.5
 - b. > 2.5
2. Change [REDACTED] in total corneal fluorescein staining at Visit 2
 - a. ≤ 3.5
 - b. > 3.5

Both strata will be entered into the IVRS/IWRS, which will assign the randomization number and the assigned kit number for the patient. The site staff will dispense to the patient the study kit labeled with the corresponding kit number. Both the randomization number and the dispensed study drug kit number will be recorded on the patient's source document and eCRF.

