If the rate of missing data for the endpoint is imbalanced between treatment groups (demonstrated by Fisher's exact test with a p-value of <0.05) and the rate of missing data for the endpoint is greater than 5% in all subjects, then the primary analyses will utilize the ITT population with observed data only using the permutation test with trimmed means methodology with Estimand 2:

Estimand 2:

- Population:
 - ITT population
- Endpoint:
 - Change from baseline [REDACTED] in total corneal fluorescein staining score in the study eye at Day 29 [REDACTED] in the ITT population
- Intercurrent event:
 - Discontinuation of study medications is ignored. Measures obtained after discontinuation of study medication will be analyzed. [treatment policy strategy]
 - Non-optimal compliance is ignored. Measures will be analyzed regardless of treatment compliance. [treatment policy strategy]

- Use of prohibited concomitant medications is ignored. Measures obtained after use of prohibited concomitant medications will be analyzed. [treatment policy strategy]
- Withdrawal or missed assessments for any reason. Missing values will be trimmed from analyses in accordance to trimmed means methodology. [hypothetical strategy]
- Population-level summary:
 - Difference in the mean change from baseline [REDACTED] in total corneal fluorescein staining score in the study eye at Day 29 [REDACTED] between 0.3% SI-614 and placebo in the ITT population.

Analyses using the ITT population with multiple imputation with Estimand 1 will be additional sensitivity analyses.

The proportion of data trimmed in the permutation test with trimmed means analysis will be dependent on the maximum rate of missing data in any treatment group using the following:

Maximum Rate of Missing Data (%)	Data Trimmed (%)
>5% to <10%	10%
10% to <20%	20%
20% to <30%	30%

In the event that the maximum rate of missing data exceeds 30% in any treatment group, then the percentage trimmed will increase by a decile until the percentage trimmed exceeds the maximum rate of missing data in any treatment group.

The ANCOVA model used to compare the change from baseline [REDACTED] to Day 29 [REDACTED] in corneal total fluorescein staining score in the study eye between 0.3% SI-614 and placebo will include baseline [REDACTED] in corneal total fluorescein staining score in the study eye at Visit 2 and treatment group as covariates.

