3.1 General Study Design

This study is a Phase 3, multicenter, randomized, double-masked study to evaluate the efficacy and safety of 0.3% SI-614 Ophthalmic Solution compared to placebo in patients with dry eye. Approximately 230 patients will be randomized with a ratio of 1:1 into one of the two groups: (1) 0.3% SI-614, or (2) placebo, which they will be instructed to administer QID for 84 days. The randomization will be stratified by two factors:

- Average of dryness and ocular discomfort at bedtime assessment based on run-in patient daily diary mean from Day-7 through Day -1: ≤ 2.5 vs > 2.5
- Change [REDACTED] in total corneal fluorescein staining at Visit 2: ≤ 3.5 vs. > 3.5

Table 1 shows the scheduled study visits, their planned study day (note that there is no Day 0 and that Day 1 corresponds to the day of randomization), and the acceptable visit window for each study visit:

Table 1. Study Visit Windows

Scheduled Visit	Planned Study Day	Visit Window
Visit 1	Day -14	± 3 Days
Visit 2	Day 1	N/A
Visit 3	Day 8	± 2 Days
Visit 4	Day 15	± 2 Days
Telephone Visit 1	Day 22	± 2 Days
Visit 5	Day 29	± 3 Days
Telephone Visit 2	Day 43	± 2 Days
Visit 6	Day 57	± 3 Days
Telephone Visit 3	Day 71	± 2 Days
Visit 7	Day 85	± 3 Days

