14.1.2 SENSITIVITY ANALYSES OF PRIMARY EFFICACY ENDPOINT

In addition to the primary analysis using Estimand 1 or Estimand 2 in ITT population, sensitivity analyses will be conducted using Estimand 1 or Estimand 2 in PP population. Analyses using observed data only will be conducted using both ITT and PP populations.

Sensitivity analyses for the primary efficacy endpoint will also be conducted using an Analysis of Variance (ANOVA) model adjusting for the stratification factors for randomization and the treatment indicator using ITT population with Estimand 1 or Estimand 2. In the ANOVA model, the randomized stratification data for the five subjects who were mis-randomized will be used. The same ANOVA model will also be performed using the correct stratification data for the five subjects.

Sensitivity analyses of the primary efficacy endpoint will also be performed on ITT population with multiple imputation by placebo group-based PMM, ITT population with multiple imputation via randomized treatment-group-based MCMC. Furthermore, a sensitivity analysis will be performed on the ITT population using last observation carried forward (LOCF) imputation where the last non-missing staining value will be carried forward (including baseline values if post-baseline values are not observed). Similar to the methods described above, the staining scores of each region will be carried forward, and then tCFS will be derived and changes from baseline will be calculated.

As an additional sensitivity analysis, tipping point analyses will be conducted to assess the robustness of the primary analyses. In tipping point analyses, a set of shift parameters will be added to the imputed missing values to re-evaluate the primary analyses conclusion under MNAR assumption. A tipping-point that overturns the statistical significance level will be identified. If the shift parameter is so extreme that it is considered clinically implausible, then this indicates robustness to missing data assumptions (MJ, Gorst-Rasmussen A, Tarp-Johansen).

Sensitivity analyses of the primary efficacy endpoint will be conducted using both ITT and PP populations.

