Table 14.2.1.2.1b	Summary of Sensitivity Analysis for Change from Baseline [REDACTED] to Day 29 [REDACTED] in Total Corneal Fluorescein Staining [REDACTED]	PP Population with Estimand 2
Table 14.2.1.2.2	Summary of Sensitivity Analysis for Change from Baseline [REDACTED] to Day 29 [REDACTED] in Total Corneal Fluorescein Staining [REDACTED]	ITT Population with PMM
Table 14.2.1.2.3	Summary of Sensitivity Analysis for Change from Baseline [REDACTED] to Day 29 [REDACTED] in Total Corneal Fluorescein Staining [REDACTED]	PP Population with PMM
Table 14.2.1.2.4	Summary of Sensitivity Analysis for Change from Baseline [REDACTED] to Day 29 [REDACTED] in Total Corneal Fluorescein Staining [REDACTED]	ITT Population with MCMC
Table 14.2.1.2.5	Summary of Sensitivity Analysis for Change from Baseline [REDACTED] to Day 29 [REDACTED] in Total Corneal Fluorescein Staining [REDACTED]	PP Population with MCMC
Table 14.2.1.2.6	Summary of Sensitivity Analysis for Change from Baseline [REDACTED] to Day 29 [REDACTED] in Total Corneal Fluorescein Staining [REDACTED]	ITT Population with LOCF

Table Number	Title	Population
Table 14.2.1.2.7	Summary of Sensitivity Analysis for Change from Baseline [REDACTED] to Day 29 [REDACTED] in Total Corneal Fluorescein Staining [REDACTED]	PP Population with LOCF
Table 14.2.1.2.8	Summary of Sensitivity Analysis for Change from Baseline [REDACTED] to Day 29 [REDACTED] in Total Corneal Fluorescein Staining [REDACTED] - Tipping Point Analysis	ITT Population
Table 14.2.1.2.9	Summary of Sensitivity Analysis for Change from Baseline [REDACTED] to Day 29 [REDACTED] in Total Corneal Fluorescein Staining [REDACTED] - Tipping Point Analysis	PP Population
Table 14.2.1.2.10	Summary of Sensitivity Analysis for Change from Baseline [REDACTED] to Day 29 [REDACTED] in Total Corneal Fluorescein Staining [REDACTED]	ITT Population with Observed Data Only
Table 14.2.1.2.11	Summary of Sensitivity Analysis for Change from Baseline [REDACTED] to Day 29 [REDACTED] in Total Corneal Fluorescein Staining [REDACTED]	PP Population with Observed Data Only
Table 14.2.1.2.12.1a	Summary of Sensitivity Analysis for Change from Baseline [REDACTED] to Day 29 [REDACTED] in Total Corneal Fluorescein Staining [REDACTED] - ANOVA Model Adjusted for the Stratification Factors Using Randomized Strata	ITT Population with Estimand 1

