Table 14.2.1.2.12.2	Summary of Sensitivity Analysis for Change from Baseline [REDACTED] to Day 29 [REDACTED] in Total Corneal Fluorescein Staining [REDACTED] - ANOVA Model Adjusted for the Stratification Factors Using the Correct Strata	ITT Population with Observed Data Only
Table 14.2.1.2.13a	Summary of Sensitivity Analysis for Change from Baseline [REDACTED] to Day 29 [REDACTED] in Total Corneal Fluorescein Staining [REDACTED] - ANOVA Model Adjusted for the Stratification Factors for Randomization	PP Population with Estimand 1

Table Number	Title	Population
Table 14.2.1.3.1a	Summary of Supportive Analyses for Change from Baseline [REDACTED] to Day 29 [REDACTED] in Total Corneal Fluorescein Staining [REDACTED] – Two-Sample t-test and Wilcoxon Rank Sum Test	ITT Population with Estimand 1
Table 14.2.1.3.2a	Summary of Supportive Analyses for Change from Baseline [REDACTED] to Day 29 [REDACTED] in Total Corneal Fluorescein Staining [REDACTED] – Two-Sample t-test and Wilcoxon Rank Sum Test	PP Population with Estimand 1
Table 14.2.1.4a	Summary of Exploratory Comparisons between Treatment Groups at Baseline and Day 29 in Total Corneal Fluorescein Staining [REDACTED]	ITT Population with Estimand 1
Table 14.2.1.5.1	Subgroup Analysis of Primary Efficacy Endpoint for Change from Baseline [REDACTED] to Day 29 [REDACTED] in Total Corneal Fluorescein Staining [REDACTED] [REDACTED] by Stratification Factor 1 – Using Randomized Correct Baseline Data	ITT Population with Observed Data Only
Table 14.2.1.5.2	Subgroup Analysis of Primary Efficacy Endpoint for Change from Baseline [REDACTED] to Day 29 [REDACTED] in Total Corneal Fluorescein Staining [REDACTED] [REDACTED] by Stratification Factor 2 – Using Randomized Correct Baseline Data	ITT Population with Observed Data Only
Table 14.2.1.5.3	Subgroup Analysis of Primary Efficacy Endpoint for Change from Baseline [REDACTED] to Day 29 [REDACTED] in Total Corneal Fluorescein Staining [REDACTED] [REDACTED] by Stratification Factor 1 – Using Randomized Stratification Data	ITT Population with Observed Data Only
Table 14.2.1.5.4	Subgroup Analysis of Primary Efficacy Endpoint for Change from Baseline [REDACTED] to Day 29 [REDACTED] in Total Corneal Fluorescein Staining [REDACTED] [REDACTED] by Stratification Factor 2 – Using Randomized Stratification Data	ITT Population with Observed Data Only

Table Number	Title	Population

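### No pooled model contains both baseline and the randomization strata, and the two ANOVA tables meant to show the effect of the five mis-stratified patients are not like for like

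*SAP*

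**What the plan says.** **Randomization.** SAP 3.1 states "The randomization will be stratified by two factors": the run-in bedtime average of dryness and ocular discomfort (≤2.5 or >2.5), and the Visit 2 change in total corneal fluorescein staining (≤3.5 or >3.5). Protocol 8.1.5 gives the same factors ("Patient's will be stratified by the following factors and cut-offs").

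**Primary model.** SAP 14.1.1 uses an "Analysis of Covariance(ANCOVA) model adjusted for baseline value with treatment group as the explanatory variable on ITT population with Estimand 1", or with Estimand 2 if that is triggered. Protocol 11.4.4 likewise names only baseline "in corneal total fluorescein staining score in the study eye at Visit 2 and treatment group as covariates".

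**Sensitivity ANOVA.** SAP 14.1.2 adds an ANOVA "model adjusting for the stratification factors for randomization and the treatment indicator using ITT population with Estimand 1 or Estimand 2". It uses the strata as randomized for the five mis-stratified patients, and then "The same ANOVA model will also be performed using the correct stratification data for the five subjects". SAP 20 says the added sensitivity and subgroup analyses are there to assess the impact of the mis-randomization on the primary endpoint.

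**Table list (SAP 21).** Table 14.2.1.2.12.1a, "ANOVA Model Adjusted for the Stratification Factors Using Randomized Strata", is ITT with Estimand 1. Table 14.2.1.2.12.2, "ANOVA Model Adjusted for the Stratification Factors Using the Correct Strata", is ITT with observed data only. Estimand 1 tables are not produced if Estimand 2 is used. Estimand 2 tables carry the suffix b, and no ANOVA table has one.

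**Other models.** The MMRM in SAP 14.2.1 has the continuous baseline symptom score but no stratum term. SAP 17 fits a baseline-adjusted ANCOVA within each level of each factor, on observed data.

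**The concern.** There are two linked problems.

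1. **Model terms.** A factor that constrains the randomization normally belongs in the analysis model. When it is left out, the between-arm balance it produces is real but is not credited in the standard error. The planned ANOVA does not fill the gap: compared with the primary ANCOVA it adds the strata and removes baseline, so a difference between the two cannot be attributed to the strata.

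2. **The mis-stratification check.** The ANOVA pair is useful only if stratum coding is the sole thing that changes. As listed, missing-data handling changes as well. If Estimand 2 is used, only one half of the pair remains. The SAP gives no rule on whether its text or its table list prevails, so programmers could follow either.

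**Working it through.** **1. The plan's own figures.** Inputs from Protocol 11.3: difference 0.75, SD 1.7, 109 per arm, two-sided 0.05, 5% dropout; secondary difference 0.13, SD 0.48.

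- Primary: SE = 1.7·√(2/109) = 0.2303, and the noncentrality is nc = 0.75/0.2303 = 3.257. Power from the noncentral t is 90.0%.
- Secondary: nc = 0.13/(0.48·√(2/109)) = 1.999. Power is 51.2%.
- Dropout: 109/0.95 = 114.7, so 115 per arm.

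These match the protocol's 90%, 51% and 115. The sample size is not in dispute, and it uses no covariate.

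**2. Which models hold which terms.**

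| Model | Baseline | Strata | Pooled |
|---|---|---|---|
| Primary ANCOVA (SAP 14.1.1) | yes | no | yes |
| Sensitivity ANOVA (SAP 14.1.2) | no | both | yes |
| Secondary MMRM (SAP 14.2.1) | symptom score, the continuous form of factor 1 | factor 2 absent | yes |
| Subgroup ANCOVA (SAP 17) | yes | one level of one factor at a time | no |

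No pooled model contains baseline and both factors.

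**3. Cost of omitting the strata from the primary model.** Let R² be the share of residual variance that the strata explain beyond baseline. The documents give no value, so a range is assumed, with 1.7 taken as the residual SD before the strata are added.

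- SE excess = 1/√(1−R²) − 1
- One-sided type I error = 1 − Φ(1.96/√(1−R²))
- Power without strata = 1 − Φ((1.96 − nc)/√(1−R²))
- Power with strata = 1 − Φ(1.96 − nc/√(1−R²))

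| R² (assumed) | SE too wide by | Type I error | Power without | Power with | Forgone (points) |
|---|---|---|---|---|---|
| 0% | 0% | 2.5% | 90.3% | 90.3% | 0 |
| 5% | 2.6% | 2.2% | 90.8% | 91.6% | 0.8 |
| 10% | 5.4% | 1.9% | 91.4% | 93.0% | 1.5 |
| 20% | 11.8% | 1.4% | 92.6% | 95.4% | 2.7 |

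(The normal approximation gives 90.3% where the t calculation gives 90.0%.)

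A simulation with permuted blocks of 4 in four equal cells, 109 per arm, agrees for R² = 0/5/10/20%:

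- Type I error without strata: 2.4/2.1/1.8/1.6%.
- Power without strata: 89.7/91.0/91.3/92.3%.
- Power with strata: 89.6/91.7/93.0/94.9%.
- Mean reported SE without strata: 0.230 to 0.231, against a true SD of the estimate of 0.231/0.226/0.219/0.209.

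For the MMRM only factor 2 is missing. If it explains 0%, 2% or 5% of residual symptom variance (assumed), including it gives power 51.6%, 52.4% or 53.6%, a gain of 0 to 2 points.

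**4. The ANOVA tables on ITT.**

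| | Estimand 1 | Estimand 2 | Observed data |
|---|---|---|---|
| Randomized strata | 14.2.1.2.12.1a | not listed | not listed |
| Correct strata | not listed | not listed | 14.2.1.2.12.2 |

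The two listed cells share neither a row nor a column. The only other ANOVA table, 14.2.1.2.13a, is PP with Estimand 1 and has no correct-strata partner.

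**5. Size of the confounding.** Recoding touches 5/230 = 2.2% of patients. Moving from Estimand 1 to observed data can touch up to 0.05 × 230 = 11.5, about 12, if the whole dropout allowance falls before Day 29.

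In an illustrative simulation (assumed stratum effects 0.4 and 0.8, residual SD 1.65, 5 of 230 recoded, complete data standing in for imputed data), recoding moved the treatment estimate by an SD of about 0.013. Dropping 5% of patients at random moved it by about 0.052. Under those assumptions the contrast between the two listed tables would mostly reflect missing-data handling.

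**The case against.** The strongest reply is that the model point is a preference.

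- Omitting the strata leaves the test valid and, if anything, conservative, and planned power is met.
- Factor 2 is derived from Visit 2 staining, which the baseline covariate may already largely carry. The redacted time points hide how much.
- 1.7 may be an unadjusted SD. If baseline explains 20% of variance (assumed), power without strata is already at least 95.4%, and the loss at R² = 5/10/20% falls to about 0.4/0.8/1.3 points.
- The present primary model is immune to how the five patients' strata are coded. Adding strata would end that.

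On the tables, the reply is that the damage is small.

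- Subgroup Tables 14.2.1.5.1 to 14.2.1.5.4 do show both codings like for like, on observed data.
- Tables 14.2.1.1a and 14.2.1.2.10 let a reader gauge the missing-data effect in the ANCOVA.
- Estimand 2 is unlikely. With 115 per arm and equal true intercurrent-event rates of 1%, 3% or 5% (assumed), the chance of meeting both triggers is below 0.01%, 0.1% or 1.2%. It reaches about 20% at 3% against 8%. In the Phase 2/3 study (Protocol 1.1) adverse events led 2 of 240 patients to discontinue, one per arm.
- About 12 is a ceiling, because the 5% covers the whole study and not only the time to Day 29.

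All of this stands as a limit on size. None of it removes either fault. The subgroup tables do not give the overall comparison that SAP 14.1.2 promises, and the mismatch between text and table list is plain on reading.

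**Conclusion.** Both parts hold. The table fault needs no assumption: SAP 14.1.2 promises one model under two stratum codings, and SAP 21 lists two tables that also differ in missing-data handling, with no Estimand 2 version of either. It concerns a sensitivity analysis for 2.2% of patients. That the missing-data change could outweigh the recoding depends on how many Day 29 values are missing.

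The model point is one of efficiency. There is no bias and no type I error inflation, and the planned 90% and 51% power are met. The power forgone is 0 to 2.7 points for the primary endpoint and 0 to 2 points for the secondary, over assumed ranges that include zero. These changes should be made, but the validity of the primary inference does not depend on them.

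**What to change.** - **SAP 14.1.1:** fit the ANCOVA with treatment, baseline staining and both stratification factors as randomized. If Estimand 2 is triggered, permute treatment labels within strata.
- **SAP 14.2.1:** add the staining-change stratum to the MMRM.
- **SAP 14.1.2:** run the corrected-strata analysis with the same model and the same imputed data sets as the randomized-strata analysis.
- **SAP 21:** change Table 14.2.1.2.12.2 to 12.2a under Estimand 1, and add 12.1b and 12.2b for Estimand 2.
- **SAP 4.1.2 and 18:** state that the five patients enter the primary model with their strata as randomized, and record the departure from the protocol's model.

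The cost is about two degrees of freedom in the primary model plus SAP and table-list wording; no new data are needed. Because the protocol-stated primary model changes, this must be settled before unmasking. The primary result would then depend on how the five patients' strata are coded, and fixing them as randomized resolves that. If the sponsor prefers to keep the primary model, the table correction should still be made, and the baseline-plus-strata ANCOVA can be added as a sensitivity analysis.
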